### 3.3.2 Exclusion Criteria

1. Participants that are not eligible for cisplatin-based chemoradiation for reasons such as chronic kidney disease, severe hearing loss, and severe peripheral neuropathy.
2. Uncontrolled inter-current illness or psychiatric illness/social situation that would limit compliance with study requirements
3. Has known hypersensitivity to cisplatin, sodium thiosulfate or any of its excipients.
4. Has profound hearing impairment at baseline and cannot hear a sound below 90 dB
5. Participants with uncompensated congestive heart failure NYHA class 3 or above.

6. Participants who cannot get secure venous access using either a Mediport or a PICC line for safe administration of intravenous sodium thiosulfate.
7. Pregnant women are excluded from this study because cisplatin is a cytotoxic agent with the potential for teratogenic or abortifacient effects. Because there is an unknown but potential risk for adverse events in nursing infants secondary to treatment of the mother with cisplatin or sodium thiosulfate, breastfeeding should be discontinued if the mother is treated with either agent.

### **3.4 Inclusion and Recruitment of Women and Minorities**

Individuals of any sex/gender, race, or ethnicity may participate.

### **3.5 Duration of Treatment**

In the absence of treatment delays due to adverse events, treatment may continue for 7 weeks or until:

- Disease progression which requires discontinuation of the study treatment;
- Inter-current illness that prevents further administration of treatment;
- Unacceptable adverse event(s);
- Participant decides to withdraw from the study;
- Significant participant non-compliance with protocol;
- If the participant meets an exclusion criterion (either newly developed or not previously; or, recognized) that precludes further study participation
- General or specific changes in the participant's condition render the participant unacceptable for further treatment in the judgment of the investigator.

### **3.6 Duration of Follow Up**

Participants will be followed for 36 months after last treatment or removal from study, or until death, whichever occurs first. Participants removed from study for unacceptable treatment or study related adverse event(s) will be followed until resolution or stabilization (as determined by the investigator) or until initiation of new anti-cancer therapy, whichever occurs first.

### **3.7 Primary Completion**

The expected primary completion is 9 months after the study opens to accrual.

### **3.8 Study Completion**

The expected study completion date is 12 months after the study opens to accrual.

## 4 Investigational Product

[figure not shown]
### 4.1 Description, Supply and Storage of Investigational Product

#### 4.1.1 Sodium Thiosulfate

##### Classification

Sodium thiosulfate has the chemical name thiosulfuric acid, disodium salt, pentahydrate. The chemical formula is  $\text{Na}_2\text{S}_2\text{O}_3 \cdot 5\text{H}_2\text{O}$  and the molecular weight is 248.17. The structural formula is:

Structure of Sodium Thiosulfate Pentahydrate

Sodium thiosulfate injection is a sterile aqueous solution and is intended for intravenous injection. Each vial contains 12.5 grams of sodium thiosulfate in 50 mL solution (250 mg/mL). Each mL also contains 2.8 mg boric acid and 4.4 mg of potassium chloride. The pH of the solution is adjusted with boric acid and/or sodium hydroxide. Sodium thiosulfate injection is a clear solution with a pH between 7.5 and 9.5.

##### Mechanism of Action

Sodium thiosulfate can reduce cisplatin-induced toxicity by scavenging reactive oxygen species, preserving the activity of antioxidant enzymes (e.g., SOD), and forming biologically inactive complexes with cisplatin to effectively reduce the systemic exposure to cisplatin. Of the thiol-containing compounds that have been shown to protect against cisplatin-induced ototoxicity, sodium thiosulfate is by far the most nucleophilic and forms complexes with cisplatin faster than any other sulfur-containing otoprotectant. The structural basis for the formation of the Pt-STS complexes has been recently described and a Pt-STS complex has been characterized as a four-coordinate Pt(II) species,  $[\text{Pt}(\text{S}_2\text{O}_3)_4]^{6-}$ , by the use of X-ray absorption spectroscopy [Metallomics 2016, 8, 1170–117610.1039/C6MT00183A]. In vitro, STS decreases the amount of free cisplatin in human plasma, with 31% of free cisplatin remaining in plasma within 10 min of STS incubation, as compared with 87% with no STS. Furthermore, the free cisplatin remains in human plasma for less than 50 min in the presence of excess STS, as compared with more than 3 h in the absence of STS.

##### Metabolism

Thiosulfate taken orally is not systemically absorbed. Most of the thiosulfate is oxidized to sulfate or is incorporated into endogenous sulphur compounds; a small proportion is excreted through the kidneys. Approximately 20-50% of exogenously administered thiosulfate is eliminated unchanged via the kidneys. After an intravenous injection of 1 g sodium thiosulfate in patients, the reported serum thiosulfate half-life was approximately 20 minutes. However, after an intravenous injection of a substantially higher dose of

sodium thiosulfate (150 mg/kg, that is, 9 g for 60 kg body weight) in normal healthy men, the reported elimination half-life was 182 minutes.

### Contraindications

None (as per the drug label)

### Formulation, Appearance, Packaging, and Labeling

Sodium thiosulfate is supplied as one 50 mL glass vial of 250 mg/mL (containing 12.5 grams of sodium thiosulfate) for intravenous administration.

### Availability

Sodium thiosulfate is being obtained as commercial supply.

### Storage and handling

Sodium thiosulfate is stored at the UCSF investigational pharmacy at controlled room temperature between 20°C and 25°C (68°F to 77°F); excursions permitted from 15 to 30°C (59 to 86°F). It needs to be protect from direct light. It should not be frozen.

### Side Effects

Complete and updated adverse event information is available in product package insert.

## **4.1.2 Cisplatin**

### Classification

Cisplatin injection infusion concentrate is a clear, colorless, sterile aqueous solution available in amber vials. The active ingredient, cisplatin, is an anti-neoplastic agent, which is yellow to orange crystalline powder with the molecular formula  $\text{PtCl}_2\text{H}_6\text{N}_2$ , and a molecular weight of 300.1. Cisplatin is a heavy metal complex containing a central atom of platinum surrounded by two chloride atoms and two ammonia molecules in the cis position. It is soluble in water or saline at 1 mg/mL and in dimethylformamide at 24 mg/mL. It has a melting point of 207° C.

### Mechanism of Action

Cisplatin crosslinks with the purine bases on the DNA and interferes with DNA repair mechanisms, causes DNA damage, and subsequently induces apoptosis in cancer cells. Although this drug seems to act as an alkylating agent, there are data to indicate that its mode and sites of action are different from those of nitrogen mustard and the standard alkylating agents.

### Metabolism

Plasma concentrations of the parent compound, cisplatin, decay monoexponentially with a half- life of about 20 to 30 minutes following bolus administrations of 50 or 100 mg/m^2 doses. Monoexponential decay and plasma half-lives of about 0.5 hour are also seen following 2-hour or 7-hour infusions of 100 mg/m^2. After the latter, the total-body clearances and volumes of distribution at steady-state for cisplatin are about 15 to 16 L/h/m^2 and 11 to 12 L/m^2.

Due to its unique chemical structure, the chlorine atoms of cisplatin are more subject to chemical displacement reactions by nucleophiles, such as water or sulfhydryl groups, than to enzyme- catalyzed metabolism. At physiological pH in the presence of 0.1M NaCl, the predominant molecular species are cisplatin and monohydroxymonochloro *cis*-diammine platinum (II) in nearly equal concentrations. The latter, combined with the possible direct displacement of the chlorine atoms by sulfhydryl groups of amino acids or proteins, accounts for the instability of cisplatin in biological matrices. The ratios of cisplatin to total free (ultrafilterable) platinum in the plasma vary considerably between patients and range from 0.5 to

1.1 after a dose of 100 mg/m^2. Cisplatin does not undergo the instantaneous and reversible binding to plasma proteins that is characteristic of normal drug-protein binding. However, the platinum from cisplatin, but not cisplatin itself, becomes bound to several plasma proteins, including albumin, transferrin, and gamma globulin. Three hours after a bolus injection and two hours after the end of a three-hour infusion, 90% of the plasma platinum is protein bound. The complexes between albumin and the platinum from cisplatin do not dissociate to a significant extent and are slowly eliminated with a minimum half-life of five days or more.

Following cisplatin doses of 20 to 120 mg/m^2, the concentrations of platinum are highest in liver, prostate, and kidney; somewhat lower in bladder, muscle, testicle, pancreas, and spleen; and lowest in bowel, adrenal, heart, lung, cerebrum, and cerebellum. Platinum is present in tissues for as long as 180 days after the last administration. With the exception of intracerebral tumors, platinum concentrations in tumors are generally somewhat lower than the concentrations in the organ where the tumor is located. Different metastatic sites in the same patient may have different platinum concentrations. Hepatic metastases have the highest platinum concentrations, but these are similar to the platinum concentrations in normal liver. Maximum red blood cell concentrations of platinum are reached within 90 to 150 minutes after a 100 mg/m^2 dose of cisplatin and decline in a biphasic manner with a terminal half-life of 36 to 47 days.

Over a dose range of 40 to 140 mg cisplatin/m^2 given as a bolus injection or as infusions varying in length from 1 hour to 24 hours, from 10% to about 40% of the administered platinum is excreted in the urine in 24 hours. Over five days following administration of 40 to 100 mg/m^2 doses given as rapid, 2- to 3-hour, or 6- to 8-hour infusions, a mean of 35% to 51% of the dosed platinum is excreted in the urine. Similar mean urinary recoveries of platinum of about 14% to 30% of the dose are found following five daily administrations of 20, 30, or 40 mg/m^2/day. Only a small percentage of the administered platinum is excreted beyond 24 hours post-infusion and most of the platinum excreted in the urine in 24 hours is excreted within the first few hours. Platinum-containing species excreted in the urine are the same as those found following the incubation of cisplatin with urine from healthy subjects, except that the proportions are different. The parent compound, cisplatin, is excreted in the urine and accounts for 13% to 17% of the dose excreted within one hour after administration of 50 mg/m^2. The mean renal clearance of cisplatin exceeds creatinine clearance and is 62 and 50 mL/min/m^2 following administration of 100 mg/m^2 as 2-hour or 6- to 7-hour infusions, respectively.

The renal clearance of free (ultrafilterable) platinum also exceeds the glomerular filtration rate indicating that cisplatin or other platinum-containing molecules are actively secreted by the kidneys. The renal clearance of free platinum is nonlinear and variable and is dependent on dose, urine flow rate, and individual variability in the extent of active secretion and possible tubular reabsorption.

There is a potential for accumulation of ultrafilterable platinum plasma concentrations whenever cisplatin is administered on a daily basis but not when dosed on an intermittent basis.

No significant relationships exist between the renal clearance of either free platinum or cisplatin and creatinine clearance.

Although small amounts of platinum are present in the bile and large intestine after administration of cisplatin, the fecal excretion of platinum appears to be insignificant.

### Contraindications

Cisplatin is contraindicated in patients with preexisting renal impairment. Cisplatin should not be employed in myelosuppressed patients, or in patients with hearing impairment. Cisplatin is contraindicated in patients with a history of allergic reactions to cisplatin or other platinum-containing compounds.

### Formulation, Appearance, Packaging, and Labeling

Cisplatin is supplied as a clear, colorless, sterile aqueous solution available in amber vials. Each 50 mL or 100 mL amber vial of infusion concentrate contains: 1 mg/mL cisplatin, 9 mg/mL sodium chloride, hydrochloric acid and sodium hydroxide to approximate pH of 4.0, and water for injection to a final volume of 50 mL or 100 mL, respectively. Cisplatin injection infusion concentrate must be further diluted prior to intravenous administration.

### Availability

Cisplatin is being obtained as commercial supply.

### Storage and handling

Cisplatin is stored at the UCSF investigational pharmacy. Reconstituted solution of cisplatin is stable for 20 hours when stored at 27°C and should be protected from light if not used within 6 hours. The vials and injection should not be refrigerated. Cisplatin has been shown to react with aluminum needles, producing a black precipitate within 30 minutes.

### Side Effects

Complete and updated adverse event information is available in the product package insert.

## **4.2 Accountability Records for Investigational Product(s)**

UCSF Investigational Drug Services (IDS) will manage drug accountability records for UCSF.

## **4.3 Ordering Investigational Product(s)**

Cisplatin and sodium thiosulfate will be obtained via commercial supply.

## **5 Treatment Plan**

### **5.1 Dosage and Administration**

Treatment will be administered on an outpatient basis.

**Table 5.1      Regimen Description**

Investigational Product	Premedication; precautions	Dose	Route	Schedule	Cycle Length
Cisplatin (weekly)	
 
Cisplatin can be given within 24 hours of radiation therapy. If radiation is held for more than 2 days (for any reason), cisplatin may be held as well until radiation resumes.
 
Prophylactic anti-emetic regimen will be given as per UCSF guidelines.
 
1 liter of isotonic fluid will be given intravenously prior to cisplatin infusion
 
	40 mg/m 	Intravenously	Days 1, 8, 15, 22, 29, 36, and 43	
Cisplatin (every-3-weeks)	
 
Cisplatin can be given within 24 hours of radiation therapy. If radiation is held for more than 2 days (for any reason), cisplatin may be held as well until radiation resumes.
 
Prophylactic anti-emetic regimen will be given as per UCSF guidelines.
 
1 liter of isotonic fluid will be given intravenously prior to cisplatin infusion
 
	80-100 mg/m 	Intravenously	Days 1, 22, and 43	Weekly or every 3 weeks
*Sodium Thiosulfate (weekly)	No contraindications	10 g/m 	Intravenously using a Mediport or a PICC line	Between 4-5 hours after each cisplatin infusion sodium thiosulfate will be	

				administered over 1-2 hours	
*Sodium Thiosulfate (every-3-week)	No contraindications	20 g/m 	Intravenously using a Mediport or a PICC line	Between 4-5 hours after each cisplatin infusion sodium thiosulfate will be administered over 1-2 hours	

\*Missed doses of sodium thiosulfate will not be replaced.

### 5.1.1 Radiation Therapy

Radiation therapy will be delivered according to the standard of care, in daily fractions of 1.8-2.2 Gy per fraction, over at least 6 weeks and no more than 7 weeks.

The maximum radiation dose to the cochlea should not exceed 45 Gy but every effort will be made to constrain the maximum dose to 35 Gy when possible without compromising tumor volume coverage. The maximum point doses and average doses delivered to the right cochlea and left cochlea will be recorded.

## 5.2 Dose Modifications for Cisplatin

### 5.2.1 Neutropenia:

If on the day of scheduled treatment with cisplatin the absolute neutrophil count (ANC) is < 1000/mm^3, hold the second chemotherapy treatment but not the radiation until ANC  $\geq$  1000/mm^3, then treat at 100% dose.

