### 5.2.2 Thrombocytopenia:

If on the day of scheduled treatment with cisplatin the platelet count is < 75,000/mm^3, hold the second chemotherapy treatment but not the radiation until platelets are  $\geq$  75,000/mm^3, then treat at 100% dose.

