### 5.2.3 Renal Adverse Events:

Cisplatin dose should be based on the serum creatinine or creatinine clearance immediately prior to the second cisplatin dose using the following guidelines:

Note: If creatinine is > 1.5 mg/dl, creatinine clearance must be calculated (Cockcroft-Gault) in order to make dose adjustment. The cisplatin dose will be determined as follows:

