#### Serum Creatinine Clearance Cisplatin Dose

- $\leq$  1.5 mg/dl or > 50 ml/min full dose
- 1.5 mg/dl and < 50 ml/min Hold drug\*

\*Cisplatin should be held (but the RT continued) and the creatinine measured weekly, until it is

- < 1.5 mg/dl or the creatinine clearance is > 50 ml/min, and then the second dose of cisplatin can be given at the reduced dose by 50%.

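### The ANC, platelet and renal rules in Sections 5.2.1–5.2.3 act on the second cisplatin dose only, although up to 7 weekly or 3 every-3-week doses are scheduled

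*Combined protocol and SAP*

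**What the plan says.** Section 5.2.1 is triggered when, "on the day of scheduled treatment with cisplatin the absolute neutrophil count" is below 1000/mm³. The action is to "hold the second chemotherapy treatment but not the radiation until ANC" has recovered, and then to treat at full dose. Section 5.2.2 has the same form for platelets below 75,000/mm³: "hold the second chemotherapy treatment but not the radiation until platelets are" back at that level.

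Section 5.2.3 bases the cisplatin dose on creatinine or creatinine clearance measured "immediately prior to the second cisplatin dose using the following guidelines". A note adds that above 1.5 mg/dl "creatinine clearance must be calculated (Cockcroft-Gault) in order to make dose adjustment". The short table that follows has a full-dose line and a hold line, "1.5 mg/dl and < 50 ml/min Hold drug" (a greater-than sign before 1.5 seems to have been lost when the text was extracted). The footnote to the hold line says "Cisplatin should be held (but the RT continued) and the creatinine measured weekly" until recovery, after which "the second dose of cisplatin can be given at the reduced dose by 50" percent.

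Table 5.1 schedules weekly cisplatin on Days 1, 8, 15, 22, 29, 36 and 43, and every-3-week cisplatin on Days 1, 22 and 43. The Study Calendar (Section 6.1) lets the treating physician omit Day 43.

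**The concern.** For ANC and platelets, the trigger and the action do not fit together. The trigger can occur on any dosing day, but the action concerns one particular dose. From the third dose on, that dose has already been given, so the instruction cannot be carried out as written.

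For renal function, the check and the restart dose are both worded for the second dose. A physician looking for the rule at weekly dose 4, for example, finds a hold line without a dose number, no stated time for the check, and a restart rule that names a different dose.

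These are operative safety rules for a drug whose nephrotoxicity the protocol itself notes (Section 1.1) and which Section 4.1.2 says should not be used in myelosuppressed patients. At stake are patient safety and consistent dosing across the 16 patients. Most weekly doses lie outside the literal wording, including most of those a weekly patient needs to meet the primary endpoint.

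**Working it through.** This is a check of wording, supported by a count of doses.

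**Step 1. Scheduled doses (Table 5.1; Day 43 footnote in Section 6.1).** Counting the listed days gives 7 weekly and 3 every-3-week doses, which matches the maxima in the Abstract. Without Day 43 there are 6 and 2.

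**Step 2. Doses after the second.** Share = (scheduled doses − 2) / scheduled doses.

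| Regimen | With Day 43 | Day 43 omitted |
|---|---|---|
| Weekly | (7 − 2)/7 = 5/7 = 71% | (6 − 2)/6 = 4/6 = 67% |
| Every 3 weeks | (3 − 2)/3 = 1/3 = 33% | (2 − 2)/2 = 0 |

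The gap is mainly one for the weekly regimen. In the every-3-week regimen it concerns only the optional Day 43 dose.

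**Step 3. Link to the primary endpoint (Section 2.2).** A weekly patient needs at least 5 administrations. At most 2 of these can be doses 1 and 2, so at least 5 − 2 = 3 are dose 3 or later.

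**Step 4. Which rules carry the dose number.**

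| Rule | Trigger or timing | Action as written | Fits dose 3 onward? |
|---|---|---|---|
| ANC (5.2.1) | Any scheduled cisplatin day | Hold the second treatment | Trigger yes, action no |
| Platelets (5.2.2) | Any scheduled cisplatin day | Hold the second treatment | Trigger yes, action no |
| Renal check (5.2.3) | Just before the second dose | Set the dose from creatinine or clearance | Not as written |
| Clearance note (5.2.3) | Creatinine above 1.5 mg/dl | Calculate clearance | Yes, no dose number |
| Renal hold line (5.2.3) | Creatinine above 1.5 mg/dl and clearance below 50 ml/min | Hold | Yes, no dose number |
| Renal restart (5.2.3 footnote) | On recovery | Second dose at a 50% reduction | Unclear |
| Nausea and vomiting (5.2.4) | Grade 3, refractory | Hold until recovery, no dose reduction | Yes, no dose number |

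The wording is therefore not uniform within Section 5.2. The general triggers, and the nausea rule without a dose number, suggest that a limit to dose 2 was not intended.

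**Step 5. Does other text close the gap?**
- Section 3.5 lets the investigator stop treatment on clinical judgment, but gives no threshold.
- The cisplatin contraindications in Section 4.1.2 advise against use in myelosuppressed or renally impaired patients, again without an ANC or platelet threshold.
- Section 5.2.5 requires adverse events to resolve to baseline or grade 1 or lower, but only when a patient switches from every-3-week to weekly dosing.
- The closing rule under Mucositis tells the investigator to take the lowest recommended dose when several adverse events give conflicting advice. It points in the conservative direction, but it is not written for a single renal event.

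None of these extends the dose-2 wording to later doses.

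**The case against.** The strongest reply is that nobody would be misled. Hematology and chemistry are drawn on every treatment day (Sections 6.1 and 6.3.2.1). The ANC and platelet rules give a threshold, a recovery level and a dose on resumption. A clinician who sees an ANC below 1000 on Day 22 of weekly dosing has one sensible course, which is to hold that day's dose. On this view the word is a leftover from drafting and no rule is missing. For ANC and platelets most of this stands: the intent is fairly plain and a practical misreading is unlikely. It makes the correction uncontroversial; it does not make the text right.

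The reply also holds in part for renal function, because the hold line and the clearance note carry no dose number. A reader might infer that patients have no renal protection after dose 2. The documents do not support that. What is missing is the stated timing of the check and a clear restart dose.

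A reader might go further and infer that the text sets two competing restart doses at weekly doses 3–7: the full 40 mg/m² from the table, or 20 mg/m² from the footnote. That reading is strained. The table is introduced by the sentence about the second dose. If that sentence limits the table, the full-dose line is limited too. If the table is general, so is the hold line, and its footnote gives only one restart dose, the 50% reduction. The split needs a general full-dose line and a footnote confined to dose 2. The fair statement is that the restart dose after dose 2 is ambiguous.

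**Conclusion.** The concern holds as a wording error in operative safety rules. Literally read, 5 of 7 weekly doses (4 of 6 without Day 43) and every-3-week dose 3 have no matching ANC or platelet hold action, no stated renal check and no clear renal restart dose. The dose counts and the wording are certain. The practical consequence is modest and rests on how literally a treating physician follows the text; most would probably hold the current dose.

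It would be tempting to infer that the trial's main result is affected. The documents do not support that. The primary endpoint counts administrations within a delay limit, so a halved dose does not directly change it. The stopping rule in Section 5.4 does use cumulative mg/m², so a restart dose could in principle enter it, but the documents give no rate of renal holds and the number of patients affected is unknown. The sample size and its stated margin of error are untouched.

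The correction should be made, at a priority suited to its limited effect.

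**What to change.** Change the object of each rule:

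- **5.2.1 and 5.2.2:** the instruction should be to hold *that scheduled cisplatin dose*, in place of the second treatment.
- **5.2.3, renal check:** time it immediately before *each cisplatin dose after the first*.
- **5.2.3, restart footnote:** say that *the next cisplatin dose* can be given at the 50% reduction. This wording is preferable to *the held dose*, which would imply that a missed weekly dose is made up.

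The cost is a few words in three subsections, made through a protocol amendment under Section 9.4. No visits or laboratory tests are added, because the blood work is already scheduled on every treatment day, and nothing in Section 8 changes.
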